During the study period (the details of which are below), participants will complete a series of questions related to self-regulation and contexts. The questions, including the momentary self-regulation questionnaire, were used in Aim 2. Participants will be asked to complete items in response to queries using mobile ecological momentary assessment (EMA); i.e., questions/questionnaires asked at a given time point outside of a laboratory setting via a mobile device. We will assess antecedent conditions prior to health risk behavior: smoking or binge eating among our smoking and binge eating samples, respectively. These antecedent conditions include mood, companionship, location, and temptation. We will offer the resources of Laddr® (a science-based behavior change intervention delivered via an interactive, self-directed mobile platform) to individuals and assess the effect of this mobile intervention system on putative targets of self-regulatory function. Laddr will also be used to deliver the EMAs to participants. Participants will use their own smartphones.

We will ask participants to respond to EMAs and to engage with the mobile intervention for 28 consecutive days. We will prompt them four times daily to inquire about health risk behavior and ask them to complete measures of self-regulation and potentially important contexts. We will send the four prompts at random times within time windows (e.g., 8–11:30 AM, 11:30 AM–3 PM, 3–6:30 PM, 6:30–10 PM). The time windows may vary based on participants' waking hours, and we will program through the software at least an hour between prompts (e.g., if a participant receives a prompt at 11 AM, he/she cannot receive another prompt until 12 PM). We will ask them to use Laddr daily to, at a minimum, update progress toward goals and complete various activities on the application that we expect will improve their self-regulation. Participants will be recommended priority therapy guides (binge eating for the binge eating sample; smoking for the smoking sample) and can also choose to engage with other guides, such as depression, anxiety, and substance use.

Participants will also be asked to use devices that allow for objective measuring of behaviors of interest. We will ask participants in the smoking sample to provide carbon monoxide (CO) samples via a breath CO meter (iCO™ Smokerlyzer®, Bedfont® Scientific Ltd.). The monitor measures breath CO in parts per million

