self-regulation and medical regimen adherence. We will examine each relationship separately prior to examining the full mechanistic model. To examine whether context is associated with level of momentary self-regulation, we will fit several multilevel models with momentary context as a predictor of momentary self-regulation measure. In Aim 2, we have identified several challenging contexts associated with worse momentary self-regulation, and we will confirm these relationships in this treatment-seeking sample of participants. The multilevel models will include a random individual-level effect to account for the non-independence of repeated observations over the 28-day period within an individual. Additionally, the models will also include a fixed effect of time to account for changes in momentary self-regulation over the treatment period. We will also consider a random individual-level slope term if there is significant variability in this change over time between individuals. Such a change in self-regulation over time may be due to the cumulative effect of Laddr use over the treatment period. We will also test whether including an interaction between context and recent Laddr usage is significant indicating Laddr use affects the association between context and momentary self-regulation. These models will identify contextual factors associated with increased or decreased momentary self-regulation.

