
Additionally, we will evaluate whether Laddr influences task behavior in our four tasks as well as fMRI activity and connectivity by comparing the pre and post scan results.

[Power and Sample Size Justification](#)

With 77 participants in each sample with up to 4 EMA responses per day for 28 days, the maximum number of observations in the momentary dataset is 8,624. However, EMA response rates are not expected to be 100%, and some participants may withdraw from the study. With 10% study drop-out and 75% EMA completion rate, the number of observations in a momentary dataset may be closer to 5,821. Even with this sample size, there will be adequate power to detect momentary relationships between contextual factors and momentary self-regulation. For example, with intraclass correlations ranging from 0.3 to 0.6, and prevalence of contexts of interest (e.g., recent exposure to smoking cue, easy food access) between 10% and 30%, there would be at least 80% power to detect differences in momentary self-regulation measures between context between 0.05-0.10 times an SD. These are small effect sizes. In the pilot data, the average SD of a momentary self-regulation measure was between 0.5 and 0.9, and the stated standardized effect sizes are equivalent to detectable mean differences

between contexts of 0.03-0.09 points on the momentary self-regulation subscales, which range from 1 to 5. Well-developed formulae for determining power to detect indirect effects within a multilevel structural equation model of intensively collected data do not exist. However, simulation studies of the bootstrap approach at the individual-level indicate that with a sample size of 71, an indirect effect with medium-sized component effects ($\beta = .39$) can be detected with 80% power.¹

¹Fritz MS, [name] DP. Required sample size to detect the mediated effect. *Psychol Sci* 2007. Mar; 18(3):233-239.

Protection of Human Participants

Potential Risks:

The potential risks associated with the data collected are low.

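### The context models adjust for time over the 28 days but not for prompt window, so a within-day course of self-regulation can bias the estimates for contexts that cluster by time of day

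*Combined protocol and SAP*

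**What the plan says.** In the Statistical Analysis Plan, the context models regress momentary self-regulation on momentary context. They include a random effect for the individual, and "the models will also include a fixed effect of time to account for changes in momentary self-regulation over the treatment period". A random slope for that change and an interaction of context with recent Laddr use are possible additions. The plan links the time term to cumulative Laddr use, and later treats time in study as a proxy for it. Time therefore most naturally means position in the 28 days.

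On sampling, Study Design states: "We will send the four prompts at random times within time windows". It lists four example windows from 8 AM to 10 PM, which may be shifted to a participant's waking hours. The same section asks smokers to give their daily CO sample in a fixed time window, so time of day is held constant there. The momentary models have no counterpart.

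Power and Sample Size Justification claims at least 80% power for "differences in momentary self-regulation measures between context between 0.05-0.10 times an SD". A significant context effect is also one of the conditions for fitting the full mediation model.

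**The concern.** The contexts named in the plan include mood, companionship, location, temptation, smoking cues and easy food access. Several of these plausibly vary over the day, and self-regulation may do so as well. Where both do, a model without time of day assigns part of the daily course to the context. The random intercept removes differences between persons, not the daily cycle within a person. A linear elapsed-time term would not remove that cycle either, even if recorded in hours.

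Two uses of the result are at stake. The plan expects these models to identify the contextual factors that go with higher or lower self-regulation. They also supply the first path of the mediation analysis, which the plan reads as self-regulation acting as a mechanism in challenging contexts. The models are powered for very small differences, so they are also sensitive to small biases.

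**Working it through.** **1. The plan's own figures.** Power and Sample Size Justification starts from "With 77 participants in each sample with up to 4 EMA responses per day for 28 days": 77 × 4 × 28 = 8,624. "With 10% study drop-out and 75% EMA completion rate" gives 8,624 × 0.90 × 0.75 = 5,821, as stated.

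For a within-person contrast in units of the total SD, with prevalence p and n = 5,821:

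detectable effect = (1.96 + 0.84) × √[(1 − ICC) / (n p (1 − p))]

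The plan works "with intraclass correlations ranging from 0.3 to 0.6" and with prevalence from 10% to 30%. It states no alpha for this calculation, so two-sided 0.05 is assumed.

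| Prevalence | ICC 0.3 | ICC 0.6 |
|---|---|---|
| 10% | 0.102 | 0.077 |
| 20% | 0.077 | 0.058 |
| 30% | 0.067 | 0.051 |

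The extremes, 0.051 and 0.102, reproduce the stated 0.05 to 0.10 SD. The lower end belongs only to 30% prevalence with ICC 0.6, so a bias should be compared with the detectable effect at its own prevalence.

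**2. Bias when the context has no effect.** Assumptions, none of them from the documents: 25% of answered prompts fall in the evening window, and self-regulation is d SD lower there for reasons that do not run through the context. Then

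size of bias = d × [P(evening | context) − P(evening | no context)]

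- 20% prevalence, strong clustering (40% in the evening, 13.3% otherwise, ratio 3): 0.25 × 0.40 / 0.20 − 0.25 × 0.60 / 0.80 = 0.500 − 0.1875 = 0.3125.
- 10% prevalence, strong clustering (20% and 6.7%, ratio 3): 0.500 − 0.222 = 0.278.
- 20% prevalence, milder clustering (30% and 16.7%, ratio 1.8): 0.375 − 0.219 = 0.156.

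**3. Size and false-positive rate.** The standard error is the detectable effect divided by 2.80. The rate is the chance that a two-sided 5% test rejects although the context has no effect.

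| Scenario | d | Bias (SD) | Rate, ICC 0.3 | Rate, ICC 0.6 |
|---|---|---|---|---|
| 20%, strong | 0.1 | 0.03 | 21% | 33% |
| | 0.2 | 0.06 | 63% | 85%* |
| | 0.3 | 0.09 | 93%* | over 99%* |
| 10%, strong | 0.1 | 0.03 | 12% | 17% |
| | 0.2 | 0.06 | 33% | 52% |
| | 0.3 | 0.08 | 63% | 85%* |
| 20%, milder | 0.1 | 0.02 | 9% | 12% |
| | 0.2 | 0.03 | 21% | 33% |
| | 0.3 | 0.05 | 40% | 62% |

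An asterisk marks a bias at or above the detectable effect for that prevalence and ICC: 4 of 18 cells. In the other 14 the rate runs from about 9% to 63%.

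**4. Another shape of daily course.** Let self-regulation fall linearly by D SD from the first to the last window. With prevalence rising from 5% to 35% over the windows, the bias is 0.26 × D, so D = 0.19 SD gives 0.05 SD. With weak clustering, 25% to 35%, it is 0.066 × D, and D must be 0.76 SD to give 0.05 SD. With no clustering it is zero. In a simulation of 69 persons with 112 prompts each, 75% answered, prevalence 5% to 35% and D = 0.2, adjusting for day only rejected in 45% (ICC 0.3) and 73% (ICC 0.6) of runs. With window added, the rate at this prevalence profile was 4 to 6%.

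**5. Price of adjusting.** The standard error rises by the factor 1/√(1 − R²), where R² is the variance of the window prevalences divided by p(1 − p). For the scenarios in step 2, in order, R² is 0.083, 0.037 and 0.021, so the increase is about 4%, 2% and 1%. With prevalences of 15, 15, 30 and 60% over the windows it is about 9%.

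**The case against.** The strongest reply is that both drivers are assumed. The documents give no daily course of self-regulation and no context prevalence by window, and weak clustering does little harm unless the daily swing is large. That stands, and it makes this a conditional point.

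Three stronger readings are tempting, and the documents do not support them:

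- A reader might infer that the spurious effect generally matches what the trial can detect, because 0.02 to 0.09 SD overlaps the stated range. That range pools prevalences and ICCs. Against the matching values, no cell with a drop of 0.1 SD and no cell with milder clustering reaches the detectable effect.
- A reader might infer that any context common in the evening will be flagged. Part of an evening drop may arise because the tested context is more frequent then. That part is a context effect, not bias. Only the remainder counts, and for some contexts it may be small.
- A reader might infer that the trial cannot tell context from time of day. Prompts are spread over four windows, so the data should allow it. Only the stated model does not.

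It can also be said that the plan claims only associations, and that it is confirming Aim 2 results. Neither reply is complete. The mediation analysis is read as a mechanism, and a daily pattern present in both studies would replicate. Over-adjustment is not a serious worry, since the software sets the prompt window and context cannot cause it.

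The effect on the mediation gate is limited. Every component relationship must be significant, and adherence is a daily outcome, so a within-day pattern bears mainly on the first path.

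**Conclusion.** The omission is in the text, and it can bias the context estimates under stated conditions. A context common at low points of the day looks harmful. One common at high points looks protective, or its true effect is masked. The result rests on an assumed evening drop of 0.1 to 0.3 SD not explained by the context, on assumed clustering ratios of 1.8 to 3, on equal response across windows, and on two-sided 5% testing.

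In that range the bias reaches the matched detectable effect only with strong clustering and a drop of 0.2 to 0.3 SD. Its wider consequence is loss of control of the false-positive rate. The plan's power figures are not in error; the question is what a significant context effect would mean. This is a cheap improvement to the model and does not point to a flaw in the data collection.

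**What to change.** Add prompt window as a fixed effect with four levels, defined relative to each participant's own windows, to the momentary context models and to the context-to-self-regulation path of the mediation model. Keep the term for time over the 28 days. Report context effects with and without the window terms, so that readers can see whether the concern is real in these data. A weekend indicator may be added on the same reasoning as a secondary refinement; no size is claimed for it here.

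The cost is SAP wording, three degrees of freedom (one more for weekend) out of about 5,821 observations, and a standard error about 1 to 9% larger for contexts that cluster by time of day. In the 10% prevalence scenario with ICC 0.3, the detectable effect moves from 0.102 to 0.104 SD. The documents do not say that the exported EMA files carry the prompt time. This is likely, since the software schedules the prompts, but the sponsor should confirm it.

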The next model will examine the relationship between level of momentary self-regulation and daily medical regimen adherence. One model for each subscale of the momentary self-regulation will be fit. In each model, momentary self-regulation will be the predictor and daily medical regimen adherence (smoking abstinence for smokers and daily physical activity for overweight/obese participants with binge eating disorder) will be the outcome. These models will identify the influence of momentary self-regulation on medical regimen adherence. Together with the previous set of models, the components of a mechanistic effect of momentary self-regulation on medical regimen adherence will be estimated. If each relationship is significant, we will fit a full multi-level structural equation model to examine the indirect effect of momentary context on medical regimen adherence as well as the direct effect of context on medical regimen adherence, independent of momentary self-regulation. Bootstrapping will be used in estimating the indirect effect in the mediation model. Bootstrapping involves taking numerous pseudo-replicate samples from the dataset and using the variability in the statistic from sample to sample to construct an interval estimate conveying the direction, magnitude, and precision

of an indirect effect. This mediation model will allow us to estimate the impact of self-regulation as a mechanism for decreased medical regimen adherence in challenging contexts.

At the individual level, we wish to examine whether Laddr can influence momentary self-regulation in a positive direction and, in turn, increase medical regimen adherence. To test this hypothesis, we will examine both the effect of time in the study on momentary self-regulation via multilevel models (e.g. linear mixed-effects models) as well as the effect of various Laddr engagement metrics on momentary self-regulation. Since Laddr use is offered as an intervention during the 28-day intervention period, time in study serves as a proxy for the cumulative effect of Laddr use. Since individuals will differ in their use of Laddr during the course of the intervention period, we will also examine Laddr engagement metrics (e.g., guides read, goals tracked) in addition to time. If Laddr usage appears to influence momentary self-regulation in a positive direction, we will again fit a multi-level structural equation model to examine both the indirect and direct effects of Laddr use on medical regimen adherence.

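### The context-by-recent-Laddr-use interaction pools within-person change with stable differences between users, so it can be significant when Laddr buffers nothing

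*Combined protocol and SAP*

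**What the plan says.** The relevant text is in the Statistical Analysis Plan section of the combined document, under the models for context and momentary self-regulation.

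- The test, and the meaning given to it: the plan will check whether "including an interaction between context and recent Laddr usage is significant indicating Laddr use affects the association" between context and momentary self-regulation.
- Random effects: "The multilevel models will include a random individual-level effect to account for the non-independence of repeated observations over the 28-day period within an individual". A second random term is optional and concerns time only: "We will also consider a random individual-level slope term if there is significant variability in this change over time between individuals". No random slope for context is named.
- Time: "the models will also include a fixed effect of time to account for changes in momentary self-regulation over the treatment period". No context-by-time term is named.
- Differences in use are expected. In the later individual-level analysis the plan says: "Since individuals will differ in their use of Laddr during the course of the intervention period, we will also examine Laddr engagement metrics". Those metrics are added alongside time in study. They are not divided into between-person and within-person parts.
- Use is not assigned. The Study Design section describes Laddr as "a science-based behavior change intervention delivered via an interactive, self-directed mobile platform". Daily use is requested, but no control or randomised level of exposure is described.

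**The concern.** Recent Laddr use varies in two ways: a given person uses it more at some times than at others, and some people use it more than others throughout. Crossing context with the raw variable gives one coefficient that averages two questions. Does context matter less when the same person has recently used Laddr? And are people who use Laddr more simply less reactive to context? The second can be true with no effect of Laddr.

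The random intercept does not separate them. It absorbs stable differences in the level of self-regulation, not in its sensitivity to context. Because context varies within person, the between-person part of the interaction also varies within person, and it is estimated with good precision.

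At stake is the statement that Laddr protects self-regulation in challenging contexts. This interaction is the test in the momentary data that addresses it. The other Laddr analyses of those data concern the level of self-regulation and the indirect path to adherence.

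**Working it through.** **1. The plan's own figures reproduce.** The Power and Sample Size Justification section gives 77 participants, 4 prompts, 28 days, 10% drop-out, 75% completion, ICC 0.3 to 0.6 and context prevalence *p* of 10% to 30%.

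- 77 × 4 × 28 = 8,624, and 8,624 × 0.90 × 0.75 = 5,821.
- Detectable context difference (two-sided 5% assumed, 80% power) = 2.80 × √[(1 − ICC) / (N p(1 − p))].
- ICC 0.6, *p* 0.3: 2.80 × √[0.4 / (5,821 × 0.21)] = 0.051 SD.
- ICC 0.3, *p* 0.1: 2.80 × √[0.7 / (5,821 × 0.09)] = 0.102 SD.

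This matches the stated 0.05 to 0.10 SD. It covers the main effect of context only. No figure is given for the interaction.

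**2. What the pooled term estimates when Laddr does nothing.** Let *s* be the between-person share of the variance in use, τ the SD of people's stable reactivity to context, and ρ the correlation of reactivity with average use. None of the three is in the documents; all values below are assumptions. With a true within-person effect of zero, the pooled coefficient per SD of use is approximately τ × ρ × √*s*.

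- τ 0.2, ρ 0.3, *s* 0.5: 0.2 × 0.3 × 0.707 = 0.042 SD (simulated 0.040 to 0.046).
- τ 0.2, ρ 0.5, *s* 0.5: 0.2 × 0.5 × 0.707 = 0.071 SD (simulated 0.067 to 0.071).

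**3. What that does to the test.** Take 69 people × 84 prompts = 5,796 observations, ICC 0.45 and context 20%. The standard error is about √[0.55 / (5,796 × 0.16)] = 0.024 SD.

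- τ 0.1, ρ 0.3, *s* 0.1: bias 0.0095, about 0.4 standard errors, so about 7% rejection.
- τ 0.2, ρ 0.3, *s* 0.5: bias 0.042, about 1.7 standard errors, so about 41%.
- τ 0.2, ρ 0.5, *s* 0.5: bias 0.071, about 2.9 standard errors, so about 83%.

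Simulation of the model as planned gives about 8% to 39% across the ρ = 0.3 settings and about 75% for the last. The formula is approximate because it ignores the extra scatter from person-to-person slopes.

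**4. Range over the plan's ICC and prevalence limits.** Simulation, 300 runs per setting, true within-person effect zero, model as written. Monte Carlo error is about 1.3 points near 5% and at most 2.9 points.

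| Reactivity SD | Correlation with use | Between-person share | False positives |
|---|---|---|---|
| 0 | 0 | 50% | 3–6% |
| 0.2 | 0 | 50% | 8–13% |
| 0.2 | 0.3 | 50% | 21–59% |
| 0.2 | 0.5 | 20% | 23–65% |
| 0.2 | 0.5 | 50% | 47–91% |
| 0.2 | 0.5 | 80% | 59–95% |
| 0.3 | 0.5 | 50% | 78–98% |

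In the second row there is no bias; the excess comes from the missing random slope for context. Adding that slope while keeping raw use still gave 13% to 69% wherever the correlation was non-zero. With use split into person mean and deviation, the context-by-deviation term rejected in 1% to 7% of runs in every setting, with mean bias within ±0.004 SD.

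**5. What the split does not remove.** In a further simulation there was no Laddr effect and there were no stable differences. The deviation in use was correlated −0.3 or −0.5 with study day, and reactivity weakened by 0.05 or 0.10 SD per SD of time (all assumed). Without a context-by-time term, the within-person term was significant in 10% to 56% of runs.

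**The case against.** The best defence is that the intent is already within-person. The variable is *recent* use, the models are introduced as momentary, and differences between people in use are handled later at the individual level. That is a fair reading of intent, but a raw recent-use variable still carries each person's average, and no centring is specified.

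Second, the bias is conditional. It needs stable reactivity to go with average use, and the documents give no evidence for or against that. This stands. A reader might infer that stable differences are bound to be taken for a Laddr effect, or that the test would be significant in most trials. The documents do not support either. Suppose reactivity falls by 0.10 or 0.15 SD per SD of a person's tendency to use Laddr, with other slope variation of SD 0.1 or none. Then rejection is about 54% to 90% at a 30% share. That assumes correlations of 0.10/√(0.10² + 0.10²) = 0.71 and 0.15/√(0.15² + 0.10²) = 0.83, or 1.0 with no other variation. At more modest correlations and shares the rates are far lower.

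Third, other planned work bears on the question: the pre/post scan comparison includes a cue task on modulating craving. That is related, but it concerns craving and not momentary self-regulation.

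Fourth, the plan hypothesises a cumulative effect of Laddr. If sustained use lowers reactivity, part of a true effect would lie between people. This also stands, and it affects how the person-mean term should be described.

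**Conclusion.** The concern holds in conditional form. The plan fixes a causal reading to one interaction that mixes within-person change with stable differences between users, and it describes use as self-directed and variable between people. The term can therefore be significant when Laddr changes nothing.

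Under the central assumptions (69 × 84 observations, ICC 0.45, context 20%, reactivity SD 0.1 to 0.2, share 10% to 50%), the false-positive rate is about 8% to 39% at correlation 0.3. It is about 75% at correlation 0.5 with share 50% and reactivity SD 0.2, and near nominal with no correlation and no variation in reactivity. These rates illustrate the risk; they do not predict this trial.

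A reader might also infer that splitting use would justify saying Laddr *affects* the association. It would not: use is not randomised, and confounding that varies over time remains. The point concerns one additional test in a single-arm mechanistic study and does not touch the main effects of context. It is worth correcting because the inference rule is explicit and the remedy is cheap.

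**What to change.** In the Statistical Analysis Plan:

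1. Define recent Laddr use and split it into the person's mean over the 28 days and the deviation from that mean.
2. Cross context with both parts, and add a random slope for context and a context-by-time term.
3. Base the statement about Laddr on the context-by-deviation term only. Say that recent use *is associated with* a weaker or stronger context effect, in place of *affects*.
4. Report the context-by-person-mean term separately, as a difference between users that may reflect either selection or a cumulative Laddr effect.

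Cost: derived variables, extra model terms and some wording; no new data. The within-person interval is wider than the pooled one, by a factor of roughly 1/√(1 − *s*): about 1.05 if 10% of the variance in use lies between people, and about 1.41 if 50% does. Any cumulative effect that shows only between people will not count as evidence of a Laddr effect.

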We propose the sample sizes above to reach 50 participants in each sample with at least 10% EMA response percentage over the duration of the four-week study (at least 12/112 EMAs). We calculated the percentage of participants who completed at least 10% of their EMAs in Aim 2 at Dartmouth. We then estimated a target sample size to reach at least 50 participants in each sample with adequate EMA participation (at least 10% completion). The proposed sample sizes account for participants who sign consent but participate minimally, and the target sample sizes of 50 for each sample with at least 10% EMA completion were determined through power calculations in Aim 2.

Statistical Analysis Plan

To evaluate the degree to which changing self-regulation is associated with changes in medical regimen adherence (measured as daily smoking abstinence in smokers and daily physical activity in overweight/obese individuals with binge eating behavior), we will fit several multilevel models (e.g., linear mixed-effects models) in addition to an overall model examining mechanistic effects. Details are provided in the following text. At the momentary level, there two relationships to be examined to understand the role of self-regulation in behavior change: the relationship between context and self-regulation, and the relationship between

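### The model of self-regulation on adherence is placed at the momentary level but has one outcome per day; row unit, within-person separation and time order are not stated, yet its significance is one of two conditions for the context mediation model

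*Combined protocol and SAP*

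**What the plan says.** The Statistical Analysis Plan introduces this model and the context model together: "At the momentary level, there two relationships to be examined to understand the role of self-regulation in behavior change". For the second relationship it states: "In each model, momentary self-regulation will be the predictor and daily medical regimen adherence" the outcome, with one model per self-regulation subscale. Study Design gives four prompts a day over 28 days and, for smokers, one breath CO sample a day in a fixed window. Adherence is defined as daily abstinence in smokers and daily physical activity in the binge eating sample.

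The clustering structure is described only in the paragraph on the context models: "The multilevel models will include a random individual-level effect to account for the non-independence of repeated observations". That paragraph also gives those models a fixed effect of time and a possible person-level slope. No day level appears.

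The plan interprets the adherence model as follows: "These models will identify the influence of momentary self-regulation on medical regimen adherence". It then sets a condition on the two component relationships: "If each relationship is significant, we will fit a full multi-level structural equation model". The indirect effect is to be bootstrapped: "Bootstrapping involves taking numerous pseudo-replicate samples from the dataset". The unit to be resampled is not named.

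**The concern.** Four choices are left open: whether a row is a prompt or a day, and how several ratings become one daily value; whether self-regulation is split into a person's usual level and the daily departure from it; whether ratings must precede the outcome; and what the bootstrap resamples.

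The choices change the answer. Copying one daily outcome onto three or four prompt rows treats it as several independent outcomes. A person-level random effect does not absorb that. Averaging to days removes the copying, but an uncentred coefficient still combines two questions: whether people with generally better self-regulation adhere more, and whether a person adheres more on better days. The plan's stated aim concerns changes in self-regulation and changes in adherence, which is the second question. At stake are the p-value that helps decide whether the context mediation model is fitted, and the claim about how self-regulation acts.

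**Working it through.** **The plan's own figures.** Power and Sample Size Justification gives 77 per sample, 4 prompts, 28 days, 10% drop-out and 75% completion.
- Maximum rows: 77 × 4 × 28 = 8,624. Expected: 8,624 × 0.90 × 0.75 = 5,821. Both reproduce.
- Detectable difference: 2.80 × √[(1 − ICC)/(5,821 × p(1 − p))], where p is context prevalence, for 80% power at two-sided 5% (assumed, as no level is stated). With "with intraclass correlations ranging from 0.3 to 0.6" and p from 10% to 30%, it runs from 2.80 × √[0.4/(5,821 × 0.21)] = 0.051 to 2.80 × √[0.7/(5,821 × 0.09)] = 0.102 SD. This matches the stated 0.05-0.10.
- That calculation is at prompt level and covers context on self-regulation only. No figure is given for self-regulation on daily adherence.

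**Number of outcomes.** 77 × 0.90 × 28 = 1,940 person-days per sample at most, so 5,821/1,940 = 3.0 rows per outcome.

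**Reading 1: prompt rows with a copied outcome.** With m prompts a day and same-day rating correlation r (assumed; not in the documents), the variance is understated by 1 + (m − 1)r. At m = 3 and r = 0.3 this is 1.6, so the true error rate is 2[1 − Φ(1.96/√1.6)] = 12.1%. At m = 4 it is 15.5%. Simulation (69 people, 28 days, 75% of prompts answered, person means removed, no true effect, 4,000 runs per setting) gave:

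| Assumed r | Prompts missed singly | Whole days missed |
|---|---|---|
| 0 | 4.6-4.8% | 4.4-4.9% |
| 0.1 | 7.3-7.6% | 8.4-9.6% |
| 0.3 | 13.3-13.6% | 15.5-16.5% |
| 0.5 | 17.0-18.4% | 21.6-22.2% |

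Each range covers a continuous and a binary outcome. A person-centred person-day model gave 4.4-5.5%. If a context effect is real and found with 80-100% power, and the two tests are independent, the condition is wrongly met in 0.8 × 13.3% to 1.0 × 13.6%, about 11-14%, at r = 0.3.

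**Reading 2: day means, uncentred.** Random-intercept model, 1,500 runs, no within-person link, the plan's ICC range, same-day correlation 0.3. With the person share of outcome variance assumed at 0.2 to 0.6, the coefficient was significant in 6-24% of runs at an assumed person-level correlation of 0.3, and in 9-56% at 0.5. At a person-level correlation of 0 the rate was about 5% (4.9% and 5.2%, outcome share 0.4). The within-person term, at outcome share 0.4, gave 4.3-6.1%.

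**Time.** Person-centring does not remove a shared trend. If rating and outcome each drift by an assumed 0.2, 0.3 or 0.5 within-person SD over 28 days with no daily link, the centred model rejects in about 5%, 7% and 24-26%. Adding time returns it to about 5%. Assumed day-to-day correlation of 0.3, 0.5 or 0.7 in both series gives 5.8%, 7.7% and 15%.

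**Direction.** Suppose self-regulation has no effect, but the day's abstinence shifts that day's ratings by an assumed 0.1 within-person SD. The centred same-day model is then significant in 21-74% of runs as assumed abstinence goes from 5% to 50% of days. Previous-day ratings, adjusted for the previous day's outcome, give 4-7%. A shared cause lasting across days (assumed day-to-day correlation 0.5, loading 0.2 or 0.3 SD) raises that to 7% and 12%.

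**The case against.** The plan commits to multilevel models for this aim, so a person-level random effect can fairly be assumed here too. A reader might infer that clustering is ignored altogether. The documents do not support that; the gap is the row unit, within-person separation and timing. A competent analyst might also aggregate to days unprompted, which would make the stacked figures irrelevant. That is possible, but nothing in the text says so, and aggregation leaves the other choices open.

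A reader might infer that day means keep the 5% error rate only if they are centred. That is too strong: with no person-level correlation the uncentred model is already at about 5%. Where such a correlation exists, the extra rejections reflect a real between-person association. They are errors only if the question is within-person. The plan's aim about changes supports that reading, although the description of the model itself does not restrict it.

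A reader might also infer that wrongly meeting the condition amounts to a false finding of mediation. It does not. It leads to a further model being fitted, whose indirect effect has its own bootstrap interval, and no error rate for that interval was computed. The condition quoted here governs only the context mediation model; the Laddr mediation model has a separate one.

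Finer data exist, since Fitbit data upload up to every 15 minutes and the prompts ask about behaviour. The plan nevertheless defines adherence as daily.

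**Conclusion.** The concern holds as a gap in specification with a real effect on a decision rule. That a momentary predictor meets a daily outcome with no stated row unit, within-person separation or time order needs no assumption. The size does: the stacked error rates depend on same-day correlation and the uncentred rates on person-level correlation and outcome share, none of which the documents give. They show what could happen and should not be read as this trial's error rate. At zero for the relevant correlation, neither problem arises.

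The same-day association cannot show direction under any choice of row, so describing it as influence goes beyond what the model can deliver and beyond the aim, which is framed as association. This should be fixed before analysis; confidence is medium because the numerical effect is unknown.

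**What to change.** 1. Analyse one row per person-day, stating how a day's ratings are combined (for example, their mean). Include a person random effect and a fixed effect of time, as in the context models, and allow for day-to-day carry-over in the errors.
2. Enter the person's mean and the daily deviation from it as separate terms. Base the condition for the context mediation model on the within-person term.
3. In the structural equation model, carry the outcome once per person-day and state that the bootstrap resamples participants.
4. Reword the claim of influence as an estimated association, and state that the same-day condition does not show direction.
5. Add a sensitivity analysis in both samples using the previous day's ratings, split the same way and adjusted for the previous day's outcome.

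The cost is SAP wording and a merge to person-days. Precision rests on at most 1,940 person-days per sample: 1,940 × (1 − 0.25⁴) = 1,933 with a rating if prompts are missed independently, or 1,940 × 0.75 = 1,455 if whole days are missed, before missing CO or activity values. The within-person correlation detectable with 80% power is 2.80/√(1,933 − 69) = 0.065 or 2.80/√(1,455 − 69) = 0.075. The lagged analysis loses day 1 (× 27/28, leaving about 1,864 or 1,403) and may show a weaker association. It informs direction but does not prove it, because a shared cause lasting across days remains.
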